## 8.2 Participant demographics/other baseline characteristics

Patient demographic and baseline characteristic data to be collected on all participants include: age, sex, race, ethnicity, type of insurance, household income and highest completed education. Relevant medical history/current medical condition data includes data collected up to the point in which informed consent is signed. Where possible, diagnoses and not symptoms, will be recorded. All medications and relevant medical histories will be recorded on the corresponding eCRFs.

## 8.3 Efficacy

[figure not shown]
The primary efficacy variables are the following:

1. Percent change from baseline in LDL-C
2. Discontinuation of statin therapy (i.e., no statin script  $\geq$  30 days before the end-of-study visit) (yes, no)

The secondary efficacy variables are the following:

1. Absolute change from baseline in LDL-C
2. Average percent change from baseline in LDL-C levels to each post-baseline visit
3. Average absolute change from baseline in LDL-C levels to each post-baseline visit
4. Achieving  $\geq$  50% reduction from baseline in LDL-C (yes, no)
5. Achieving LDL-C  $<$  100 mg/dL (yes, no) (among the subset of participants with LDL-C  $\geq$  100 mg/dL at baseline)

6. Achieving LDL-C < 70 mg/dL (yes/no)
7. Achieving LDL-C < 55 mg/dL (yes, no)
8. Percent change from baseline in apoB
9. Absolute change from baseline in apoB
10. Percent change from baseline in non-HDL-C
11. Absolute change from baseline in non-HDL-C
12. Percent change from baseline in VLDL-C
13. Absolute change from baseline in VLDL-C
14. Percent change from baseline in total cholesterol
15. Absolute change from baseline in total cholesterol
16. Percent change from baseline in Lp(a)
17. Absolute change from baseline in Lp(a)
18. Percent change from baseline in HDL-C
19. Absolute change from baseline in HDL-C
20. Percent change from baseline in triglycerides
21. Absolute change from baseline in triglycerides
22. Intensity of lipid-lowering therapy (decrease in dose, no change in dose, increase in dose)
23. Proportion of days covered (total number of days on either statin, ezetimibe, bempedoic acid or PCSK9 inhibiting monoclonal antibody therapies prescribed divided by total number of study days)

### 8.3.1 Primary efficacy assessments

The primary efficacy assessments will be LDL-C and discontinuation of statin therapy. Samples for LDL-C will be collected at screening (Visit 1) and on visit days 2, 3, 4, 5 and 6 (Table 8-1).

### **8.3.2 Other efficacy assessments**

Other efficacy assessments will include measurement of Apolipoprotein B, Lp(a), non-HDL-C, VLDL-C, total cholesterol, triglycerides, and HDL-C. Samples for these additional efficacy biomarkers will be collected at Visits 1, 2, 3, 4, 5 and 6 ([Table 8-1](#)).

### **8.3.3 Appropriateness of efficacy assessments**

The assessment of lipids and lipoproteins is standard in both clinical practice and in trials evaluating the efficacy of lipid-modifying therapies ([Grundy et al 2019](#)). Utilization of other therapies (including, but not limited to, statin discontinuation, adherence to therapies and changes in therapy) are frequently used variables to evaluate the effectiveness of therapies in clinical studies. The patient-reported outcomes instruments used in this study are validated instruments that have been previously used in clinical trials.

## **8.4 Safety**

Safety assessments will consist of monitoring and recording of all adverse events and serious adverse events, evaluation of hematology, blood chemistry and urine values, regular measurement of vital signs and the performance of physical examinations.

As per [Section 4.6](#), during a Public Health Emergency that limits or prevents on-site study visits, regular phone or virtual calls should occur for safety monitoring and discussion of the participant's health status until the participant can again visit the site. If a participant cannot visit the site to have pregnancy tests done, a home urine pregnancy test kit may be used. Participants can perform the urine pregnancy test at home at the time of the scheduled visit and report the result to the site, or a communication process should be established with the participant so that the site is informed of the pregnancy test results. If a visit by site staff or home nursing staff is arranged, it is important that participants are instructed to perform the urine pregnancy test first and only if the test result is negative proceed with the administration of the study treatment.

Safety assessments are specified below with the assessment schedule detailing when each assessment is to be performed.

For details on AE collection and reporting, refer to AE section. Please consult the Investigator's Brochure for the specific (non-routine) safety assessments.

**Table 8-2 Safety Assessment**

Assessment	Specification
Physical examination	
A complete physical examination will be performed at Visits 1 and 6. It will include the examination of general appearance, skin, neck (including thyroid), eyes, ears, nose, throat, lungs, heart, abdomen, back, lymph nodes, extremities, vascular, and neurological examinations. If indicated based on medical history and/or symptoms, rectal, external genitalia, breast, and pelvic exams will be performed. Visits 3, 4 and 5 physical exams will be a limited/focused examination.
 
Information for all physical examinations must be included in the source documentation at the study site. Clinically relevant findings that are present prior to signing informed consent must be recorded on the appropriate eCRF that captures medical history. Significant findings made after signing informed consent which meet the definition of an Adverse Event must be recorded as an adverse event.

Vital signs	
Vital signs will be assessed at Visits 1, 2, 3, 4, 5 and 6. This will include blood pressure and pulse measurements. BP will be measured using a standard sphygmomanometer with an appropriate sized cuff and the non- dominant arm in the sitting position after 5 minutes of rest. Every effort should be made to use the same arm for the participant for all vital signs assessments and where possible, the same person doing the assessment.

Height and weight	
Height in centimeters if possible will be measured at Visits 1 and 2. Body weight to the nearest 0.1 kg without shoes, will be measured at Visits 1, 2, 3, 4, 5 and 6.

#### **8.4.1 Laboratory evaluations**

Specimens will be obtained at the time points in the Assessment Schedule ([Table 8-1](#)).

A central laboratory will be used for analysis of all specimens collected, with the exception of urine pregnancy tests and urine dipstick tests, which will be done locally (using testing materials supplied by the central laboratory). Serum pregnancy tests at screening will be done by the central laboratory. Details on the collections, shipment of samples and reporting of results by the central laboratory are provided to investigators in a Laboratory Manual.

Clinically significant abnormalities must be recorded as either medical history/current medical conditions or adverse events as appropriate.

Clinically notable laboratory findings are defined in [Section 16.1](#)

Local laboratory assessments may be performed on an as-needed basis for unscheduled visits. Laboratory values that exceed the boundaries of a notable laboratory abnormality must be commented on by the investigator on the source document and additional laboratory evaluations should be performed, as judged appropriate by the investigator. If the laboratory abnormality induces clinical signs or symptoms, or requires therapeutic intervention, then the diagnosis or medical condition must be entered on the patient's AE eCRF. If the laboratory abnormality is the primary reason for an unforeseen hospitalization or otherwise fulfills the seriousness category of an AE, then the procedure for rapid notification of SAEs must be followed. Likewise, if the laboratory abnormality leads to discontinuation from the study drug (temporarily or permanently), the patient must be followed until the abnormality resolves or until it is judged to be permanent. This investigation may include continued monitoring by repeat laboratory testing or by performing additional laboratory tests as deemed necessary by the investigator or the Novartis medical monitor.

As per [Section 4.6](#), during a Public Health Emergency that limits or prevents on-site study visits, if a visit by site staff/home nursing staff is arranged, specimen samples should be collected during the visit and processed and handled in line with the study laboratory manual.

#### **8.4.1.1 Hematology**

Blood draws for hematology will include:

Hemoglobin, hematocrit, erythrocytes, reticulocytes, mean cell hemoglobin (MCH), mean corpuscular volume (MCV), mean corpuscular hemoglobin concentration (MCHC), platelet count, white blood cell count with differential.

#### **8.4.1.2 Coagulation**

Blood draws for coagulation will include:

Prothrombin time (PT), international normalized ratio (INR), activated partial thromboplastin (aPTT).

#### **8.4.1.3 Chemistry**

Blood draws for chemistry will be performed per the Schedule of Assessments ([Table 8-1](#)). Analysis will vary based on visit day as follows:

- **Full serum chemistry:** AST, ALT, alkaline phosphatase (ALP), gamma glutamyl transferase (GGT), total bilirubin (TBL), direct and indirect bilirubin, creatine phosphokinase (CPK), lactate dehydrogenase, bicarbonate, uric acid, creatinine, urea (BUN), estimated glomerular filtration rate (eGFR), hsCRP, sodium, potassium, magnesium, calcium, inorganic phosphate, chloride, albumin, total protein, hsCRP, glucose (fasting), [REDACTED]
- **Limited serum chemistry: ONLY:** AST, ALT, ALP, GGT, TBL, CPK, creatinine, eGFR, fasting glucose, hsCRP and [REDACTED].

#### **8.4.1.4 Urinalysis**

Urinalysis will be performed in accordance with the assessment schedule ([Table 8-1](#)) at the investigational site (a standardized dipstick test will be supplied by the Central Laboratory). Urinalysis will be performed from a sample of mid-stream urine. In case of abnormal results, microscopy and other assessments will be performed at the local laboratory and the abnormality recorded as an AE.

The following parameters will be assessed: pH, specific gravity, presence of blood, protein, glucose, ketones, nitrates, leukocyte esterase, uro-bilinogen and bilirubin. Microscopic panel will be only performed in the event of abnormalities (Red Blood Cells, White Blood Cells, Casts, Crystals, Bacteria, Epithelial cells).

#### **8.4.1.5 Hepatitis markers**

Hepatitis markers will be evaluated at screening only, and will include HBV-DNA, HBsAg, HBsAb, HBcAb and HCV RNA-PCR. Testing will be performed in a test sequence recommended by the Centers for Disease Control and Prevention.

#### **8.4.2 Electrocardiogram (ECG)**

A standard 12 lead ECG will be performed at Visit 1. Interpretation of the tracing must be made by a qualified physician and documented on the ECG section of the eCRF. Each ECG tracing should be labeled with the study, participant number and date and kept in the source documents at the study site.

Clinically significant abnormalities must be recorded on the eCRF as either medical history and/or adverse events as appropriate.

#### **8.4.3 Pregnancy and assessments of fertility**

All pre-menopausal women who are not surgically sterile will have a serum pregnancy test (hCG) performed at visit 1 (central lab). In addition, these participants will have a urine pregnancy test conducted in the local laboratory at visits 2, 3, 4, 5 and 6. If any of these tests are positive at Visits 1 and/or 2, the participant should not be enrolled in the trial. If a participant tests positive at Visits 3, 4 or 5, or should become pregnant during the trial, the participant may remain in the trial for follow-up visits, but cannot continue to receive inclisiran injections.

During a Public Health Emergency that limits or prevents on-site study visits, a urine home pregnancy test kit may be used. Relevant participants can perform the urine pregnancy test at home and report the result to the site. If a visit by site staff/home nursing staff is arranged, it is important that participants perform the urine pregnancy test first, and only if the test result is negative, proceed with the administration of the study treatment.

#### **8.4.4 Other safety evaluations**

##### **8.4.4.1 Anaphylactic reactions**

Potential anaphylactic reactions should be assessed by Sampson criteria in [Section 16.4 \(Appendix 4\)](#).

#### 8.4.4.2 Injection site reactions

Injection site reactions (ISRs) should be monitored at each visit from the randomization visit onwards and through additional contacts with the participant between visits as needed. ISRs including individual signs or symptoms at the injection site following study treatment administration should be recorded on an appropriate eCRF page. Every effort should be made to follow up with the participant until resolution of the ISR.

#### 8.4.4.3 Hyperglycemia-related events

Laboratory results and newly added concomitant medications should be checked for potential hyperglycemia-related AEs.

‘New onset of diabetes’ should be reported as AE on the eCRF in participants with no medical history of diabetes when:

█ [REDACTED]

- If a new concomitant medication for control of plasma glucose is added, further information to assess for a diagnosis of new onset diabetes will need to be collected

‘Worsening of glycemic control’ should be reported as AE on the eCRF in participants with a medical history of diabetes ( [REDACTED] ) when:

█ [REDACTED]

- New concomitant medication or increase in dose of current antidiabetic therapy is initiated to improve the control of plasma glucose level

#### 8.4.5 Appropriateness of safety measurements

The safety assessments selected are standard for the evaluation of patients with atherosclerotic cardiovascular disease and elevated LDL-C.

### 8.5 Additional assessments

No additional tests will be performed on participants entered into this study.

[REDACTED]

█ [REDACTED]

[REDACTED]

[REDACTED]

[REDACTED]

[REDACTED]

[REDACTED]

[REDACTED]

[REDACTED]

[REDACTED]

### **8.5.3.3 HealthiVibe Optional Trial Feedback Questionnaire**

This study includes an optional questionnaire, the “Trial Feedback Questionnaire” for participants to provide feedback on their clinical trial experience. Individual trial participant responses will not be reviewed by investigators. Responses may be used by the sponsor (Novartis) to understand where improvements can be made in the clinical trial process. This questionnaire does not ask questions about the trial participant's disease, symptoms, treatment effect, or adverse events, and, therefore is not considered as trial data.

## **9 Study discontinuation and completion**

### **9.1 Discontinuation and completion**

#### **9.1.1 Study treatment discontinuation and study discontinuation**

Discontinuation of study treatment for a participant occurs when study treatment is stopped earlier than the protocol planned duration and can be initiated by either the participant or the investigator.

The investigator must discontinue study treatment for a given participant if, he/she believes that continuation would negatively impact the participant's well-being.

Study treatment must be discontinued under the following circumstances:

- Participant/guardian decision
- Pregnancy
- Use of prohibited treatment as per recommendations in the prohibited treatment section
- Any situation in which study participation might result in a safety risk to the participant
- Any severe suspected drug related AE at the investigator's discretion

If discontinuation of study treatment occurs, the investigator should make a reasonable effort to understand the primary reason for the participant's premature discontinuation of study treatment and record this information.

Participants who discontinue study treatment or who decide they do not wish to participate in the study further should NOT be considered withdrawn from the study UNLESS they withdraw their consent (see 'Withdrawal of Informed Consent' section). **Where possible, they should return for the assessments indicated** in the Assessment Schedule. If they fail to return for these assessments for unknown reasons, every effort (e.g. telephone, e-mail, letter) should be made to contact the participant/pre-designated contact as specified in the lost to follow-up section. This contact should preferably be done according to the study visit schedule. Unless a participant withdraws informed consent, personal and coded data are able to be collected in accordance with the informed consent form.

If the participant cannot or is unwilling to attend any visit(s), the site staff should maintain regular telephone contact with the participant, or with a person pre-designated by the participant. This telephone contact should preferably be done according to the study visit schedule.

After study treatment discontinuation, at a minimum, in abbreviated visits, the following data should be collected at clinic visits or via telephone/email contact:

- New / concomitant treatments
- Adverse Events / Serious Adverse Events

The investigator must also contact the IRT to register the participant's discontinuation from study treatment.

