## Glossary of terms

Additional treatment	Medicinal products that may be used during the clinical trial as described in the protocol, but not as an investigational medicinal product (e.g. any background therapy)
Assessment	A procedure used to generate data required by the study
Biologic Samples	A biological specimen including, for example, blood (plasma, serum), saliva, tissue, urine, stool, etc. taken from a study participant
Clinical Trial Team	A group of people responsible for the planning, execution and reporting of all clinical trial activities. Examples of team members include the Study Lead, Medical Monitor, Trial Statistician etc.
Coded Data	Personal Data which has been de-identified by the investigative center team by replacing personal identifiers with a code.
Cohort	A specific group of participants fulfilling certain criteria and generally treated at the same time
Control drug	A study drug (active or placebo) used as a comparator to reduce assessment bias, preserve blinding of investigational drug, assess internal study validity, and/or evaluate comparative effects of the investigational drug
Discontinuation from study	Point/time when the participant permanently stops receiving the study treatment and further protocol required assessments or follow-up, for any reason. No specific request is made to stop the use of their samples or data.
Discontinuation from study treatment	Point/time when the participant permanently stops receiving the study treatment for any reason (prior to the planned completion of study drug administration, if any). Participant agrees to the other protocol required assessments including follow-up. No specific request is made to stop the use of their samples or data.
Dosage	Dose of the study treatment given to the participant in a time unit (e.g. 100 mg once a day, 75 mg twice a day)
Electronic Data Capture (EDC)	Electronic data capture (EDC) is the electronic acquisition of clinical study data using data collection systems, such as Web-based applications, interactive voice response systems and clinical laboratory interfaces. EDC includes the use of Electronic Case Report Forms (eCRFs) which are used to capture data transcribed from paper source forms used at the point of care
End of the clinical trial	The end of the clinical trial is defined as the last visit of the last participant or at a later point in time as defined by the protocol

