Period	The subdivisions of the trial design (e.g. Screening, Treatment, Follow-up) which are described in the Protocol. Periods define the study phases and will be used in clinical trial database setup and eventually in analysis
Personal data	Participant information collected by the Investigator that is coded and transferred to Novartis for the purpose of the clinical trial. This data includes participant identifier information, study information and biological samples.
Premature participant withdrawal	Point/time when the participant exits from the study prior to the planned completion of all study drug administration and/or assessments; at this time all study drug administration is discontinued and no further assessments are planned
Randomization	The process of assigning trial participants to investigational drug or control/comparator drug using an element of chance to determine the assignments in order to reduce bias.
Randomization number	A unique identifier assigned to each randomized participant
Re-screening	If a participant fails the initial screening and is considered as a Screen Failure, he/she can be invited once for a new Screening visit after medical judgment and as specified by the protocol

Remote	Describes any trial activities performed at a location that is not the investigative site where the investigator will conduct the trial, but is for example a home or another appropriate location
Screen Failure	A participant who did not meet one or more criteria that were required for participation in the study
Source Data/Document	Source data refers to the initial record, document, or primary location from where data comes. The data source can be a database, a dataset, a spreadsheet or even hard-coded data, such as paper or eSource
Start of the clinical trial	The start of the clinical trial is defined as the signature of the informed consent by the first participant
Study treatment	Any drug or combination of drugs or intervention administered to the study participants as part of the required study procedures; includes investigational drug(s), control(s) or background therapy
Study treatment discontinuation	When the participant permanently stops taking any of the study drug(s) prior to the defined study treatment completion date (if any) for any reason; may or may not also be the point/time of study discontinuation

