## 8 Visit schedule and assessments

The Assessment Schedule ([Table 8-1](#)) lists the assessments when they are performed. All data obtained from these assessments must be supported in the participant’s source documentation.

Participants should be seen for all visits/assessments as outlined in the assessment schedule ([Table 8-1](#)) or as close to the designated day/time as possible (+/- 7 days). Missed or rescheduled visits should not lead to automatic discontinuation. Participants may be seen at

any time for an unscheduled visit, e.g., if they experience deterioration or AEs that in the opinion of the Investigator/qualified site staff requires closer monitoring.

Participants who discontinue from study treatment should continue to attend the remaining study visits as indicated in the Assessment Schedule ([Table 8-1](#)).

Participants who discontinue from study or withdraw their consent should be scheduled for a final evaluation visit if they agree, as soon as possible, at which time all of the assessments listed for the final visit will be performed. At this final visit, all investigational product should be reconciled, and the adverse event and concomitant medications not previously reported must be recorded on the eCRF.

Participants will have to comply with the following restrictions during the study:

- Participants need to fast for at least 8 hours for all visits (measurement of lipids/lipoproteins and blood glucose requires participants to be fasting). If the participant has not fasted, the collection of laboratory evaluations must be rescheduled.
- Blood donation will not be allowed at any time during the study

The “X” in the table denotes the assessments to be recorded in the clinical database or received electronically from a vendor. The “S” in the table denotes the assessments that are only in the participant’s source documentation and do not need to be recorded in the clinical database.

As per [Section 4.6](#), during a Public Health Emergency that limits or prevents on-site study visits, alternative methods of providing continuing care may be implemented by the Investigator as the situation dictates. If allowable by a local Health Authority and depending on operational capabilities, phone calls, virtual contacts (e.g. tele consult) or visits by site staff/ home nursing staff to the participant’s home, can replace on-site study visits, for the duration of the disruption until it is safe for the participant to visit the site again.

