Data collected at scheduled or unscheduled visits will be used in the analysis if they fall into an analysis window for an analysis visit. If more than one visit (scheduled or unscheduled) is made within the window specified above for any analysis visit, the non-missing assessment closest to the target study day will be used in the analysis for that visit. In the case of tied visits, non-missing data from the later visit will be used. In the case of identical collection dates and times, the average of the two visits will be used. However, all data will be included in the participant data listings.

Last Visit Summaries

The protocol uses the term End of Study (EOS) for Day 330. If a participant discontinues from the study early, they will have an early termination visit that is before Day 330. Using the windowing provided in [Table 2-2](#), the early termination visit will be assigned to the nearest analysis visit. Tables that summarize data by visit will include data by analysis visit (Baseline, Day 90, Day 180, Day 270, and Day 330) along with a Day 330/Last Visit which will combine data from Day 330 for those participants who have data collected within the Day 330 analysis window with the data from the last post-baseline visit for those participants who do not have data collected in the Day 330 analysis window.

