2.5.1 Primary endpoint(s)

The primary efficacy variables are the following:

1. Percent change from baseline in LDL-C
2. Discontinuation of statin therapy (i.e., no statin use \geq 30 days before the end-of-study visit) (yes, no)

The primary analysis time point for both primary efficacy variables is at Day 330.

The following provides additional details on the derivation of primary efficacy variable 2.

If a participant is considered a study completer and has a non-missing visit date for the nominal Day 330 visit recorded, a statin assessment date (to assess if the participant was taking statins at this point in time) will be calculated by subtracting 30 days from the Day 330 visit date (e.g., study Day 300 if the participant completes on study Day 330). The statin assessment date will be compared to the maximum statin end date of all statin medications taken by the participant. If the last statin is recorded as ongoing at study end date, the maximum statin end date will be set to the study end date.

- If the participant was on a statin on or after this statin assessment day (maximum statin end date \geq statin assessment date), the participant will be considered as discontinued statin = 'no.'
- If the participant was not on a statin on and after this statin assessment day (maximum statin end date $<$ statin assessment date), or they were a completer who did not have a Day 330 visit, the participant will be considered as discontinued statin = 'yes.'

All early termination participants will be considered to not be on a statin for this endpoint (the participant will be considered as discontinued statin = 'yes').

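### For a participant who leaves without withdrawing consent, Protocol Section 8 and the glossary close follow-up while 9.1.1 keeps it open, and SAP 2.5.1 turns the resulting status into a statin-discontinuation event

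*Protocol*

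**What the plan says.** The participant in question no longer wishes to take part but does not withdraw consent. Protocol 9.1.2 reserves consent withdrawal for someone who refuses both participation and further study contact, so this is a separate status.

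- **Protocol 9.1.1:** participants "who decide they do not wish to participate in the study further should NOT be considered withdrawn from the study UNLESS they withdraw their consent". It adds: "Where possible, they should return for the assessments indicated". If they will not attend, sites should keep up telephone contact, preferably on the visit schedule. The minimum data after treatment discontinuation are new or concomitant treatments and adverse events.
- **Protocol Section 8:** "Participants who discontinue from study or withdraw their consent should be scheduled for a final evaluation visit if they agree, as soon as possible". All final-visit assessments are then done.
- **Protocol glossary:** discontinuation from study is the point when the participant "permanently stops receiving the study treatment and further protocol required assessments or follow-up, for any reason". The entry for premature participant withdrawal says that "at this time all study drug administration is discontinued and no further assessments are planned".
- **Protocol 12.4.2 and SAP 2.5.2:** all efforts will be made to follow participants to the end of the study.
- **SAP 2.1.1:** "If a participant discontinues from the study early, they will have an early termination visit that is before Day 330". That visit is assigned to the nearest analysis visit. The Day 330 window is study days 301 to 375.
- **SAP 2.5.1:** "All early termination participants will be considered to not be on a statin for this endpoint". A completer without a Day 330 visit is also coded as having discontinued.
- **SAP 2.5.4:** a participant is assumed to have discontinued statins only where current statin use cannot be ascertained.

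**The concern.** Two sites facing the same participant can follow the protocol and produce different data. One books an early final evaluation and completes the exit page. The other keeps the participant in the study and tries to obtain Day 330 information.

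Both primary estimands ignore discontinuation of study treatment, so they rely on Day 330 data from people who drift away. For LDL-C, a final visit before study day 301 falls outside the Day 330 window, so the mixed model has no Day 330 value for that person. For statin discontinuation, early-termination status alone makes the person an event, even with a statin recorded as ongoing at exit.

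The trial is open-label and only one arm receives study drug, so leaving could plausibly differ by arm. If it does, administrative exit status feeds directly into the non-inferiority difference. Equal exits matter too: adding events to both arms pulls a true difference towards zero, which favours non-inferiority.

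**Working it through.** **1. The two rules side by side**

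| | Section 8 and glossary | Section 9.1.1 |
|---|---|---|
| Status | Discontinued from study | Not withdrawn |
| Next step | Final evaluation soon, if the participant agrees (Section 8); follow-up ends (glossary) | Scheduled visits where possible, otherwise telephone |
| Day 330 LDL-C | None if the final visit is before study day 301 | Possible if the participant will attend or give a sample |
| Day 330 statin status | Not sought; coded as discontinued | Obtainable by telephone, but SAP 2.5.1 may still code it as discontinued |

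The documents agree about people who stop study treatment only: Section 8 and 9.1.1 both keep them on schedule. The conflict is confined to leaving the study without withdrawing consent.

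**2. The plan's own sample size**

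Inputs (Protocol 12.8.1, SAP Section 3): one-sided 0.0125 (z = 2.2414), power 0.90 (z = 1.2816), margin 0.15, rate 0.20 in each arm.

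n per arm = (2.2414 + 1.2816)² × 2 × 0.20 × 0.80 / 0.15² = 176.5, so 177 per arm and 354 in total. This matches the plan. Inflation: 354 / 0.80 = 442.5, against 444 stated. The sample size is not in question.

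**3. Effect of coding leavers as events**

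Assumptions:
- 200 per arm (222 less the planned 10% statin-intolerant = 199.8);
- true rates 0.20 (usual care) and 0.35 (inclisiran first), so the true difference sits on the margin;
- leavers stop statins at their arm's true rate, and all are coded as discontinued;
- exit fraction e by arm. The documents give only 10% loss overall, with no split by arm or reason.

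Formulas: observed p = p + e(1 − p); SE = √[p₁(1 − p₁)/200 + p₂(1 − p₂)/200]; P(declare) = Φ((0.15 − d)/SE − 2.2414).

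| Exits, usual care / inclisiran first | Observed rates | d | SE | P(false non-inferiority) |
|---|---|---|---|---|
| 0 / 0 | 0.200, 0.350 | 0.1500 | 0.0440 | 1.25% |
| 5% / 5% | 0.240, 0.3825 | 0.1425 | 0.0457 | 1.9% |
| 6% / 4% | 0.248, 0.376 | 0.1280 | 0.0459 | 3.9% |
| 7% / 3% | 0.256, 0.3695 | 0.1135 | 0.0460 | 7.4% |
| 3% / 7% | 0.224, 0.3955 | 0.1715 | 0.0454 | 0.3% |

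Worked case, 7%/3%: 0.20 + 0.07 × 0.80 = 0.256; 0.35 + 0.03 × 0.65 = 0.3695; (0.15 − 0.1135)/0.0460 − 2.2414 = −1.448; Φ = 0.0738.

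**4. If the true rates are equal at 0.20**

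The same formula gives power of 93.4% with no exits, 89.8% with 5%/5%, and 70.0% with 3% usual care and 7% inclisiran first.

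**5. LDL-C**

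With difference 15, SD 40 and two-sided 0.025, power is Φ(15/(40√(2/n)) − 2.2414). This is 95.6% with 222 per arm and 93.4% with 200 per arm, so power barely moves. The cost is heavier reliance on the missing-at-random assumption.

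**The case against.** The passages are partly compatible. Section 8 schedules a final evaluation but does not forbid later telephone contact. The glossary describes a state and does not tell sites to stop trying, and both documents state the intent to follow everyone to the end. The SAP sentence on early termination visits also covers consent withdrawal, so it need not be a choice of Section 8 over 9.1.1. This has some force, but it does not settle the matter. Section 8 treats leaving the study separately from stopping treatment and attaches close-out steps to it, and no passage says that 9.1.1 prevails.

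Three stronger readings are tempting, and the documents do not support them:

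- **That 9.1.1 compels scheduled follow-up.** Its wording is conditional ("Where possible, they should return for the assessments indicated"). A participant who refuses visits and sampling has no Day 330 LDL-C under either rule. The documents do not size the group still willing to be sampled.
- **That following 9.1.1 alone restores the 1.25% error rate.** The inflation comes from the coding in SAP 2.5.1, which also counts a completer without a Day 330 visit as discontinued. A participant followed only by telephone could be coded exactly as one closed out early. The nominal rate returns only if ascertained status is used.
- **That 7.4% is the expected error.** It needs a true difference on the margin and more than twice as many exits in usual care. The reverse split is conservative.

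**Conclusion.** The contradiction is real and unresolved for participants who leave without withdrawing consent. It matters because the SAP converts exit status into a co-primary outcome, and because SAP 2.5.1 overrides known statin use whereas 2.5.4 would assume discontinuation only when status cannot be ascertained.

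The size is uncertain. Under the stated assumptions, false non-inferiority ranges from 0.3% to 7.4% across splits of 10 percentage points of exits between the arms, and is 1.9% when they are equal. Those figures belong to the coding rule combined with early close-out, not to the protocol contradiction alone. They assume that every modelled leaver goes without withdrawing consent and is closed out; if fewer do, the shift from 1.25% is smaller for the same balance between arms. The LDL-C consequence is limited to willing attenders and has little effect on power.

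The plan should be changed: the remedy is cheap and protects a non-inferiority endpoint in an open-label trial.

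**What to change.** 1. **Protocol Section 8 and glossary.** Make 9.1.1 the governing rule. State that a participant who stops attending without withdrawing consent stays in follow-up to Day 330 by visit, home draw or telephone, where they agree. Keep the voluntary early final evaluation, and say that it does not end follow-up.
2. **Protocol 9.1.2.** Reconcile it with Section 8. It says both that no further assessments are conducted after consent withdrawal and that a final evaluation should be made.
3. **Study Completion/Exit page.** For these participants, complete it only at the Day 330 contact or after the lost-to-follow-up diligence in 9.1.3.
4. **SAP 2.1.1 and 2.5.1.** Define early termination as consent withdrawal, death, confirmed loss to follow-up or sponsor termination. Use statin status ascertained at a Day 330 contact, including by telephone, EHR or claims, whether or not a Day 330 visit took place. Impute discontinuation only when status cannot be ascertained, as 2.5.4 already states.

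The cost is minor wording changes in both documents and slightly more data derivation for statin status. Telephone contact and collection of concomitant treatments are already in 9.1.1, and EHR and claims data are already planned sources. The SAP change should be made before database lock.
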